## A. SPECIFIC AIMS

### **Chronic opioid treatment for chronic pain has led to widespread opioid dependence.**

Prescription of opioid medications for treatment of chronic non-cancer pain rose significantly in the 1990s and 2000s. At the prescribing peak of 2010, prescriptions outnumbered persons in many parts of the country, and this continues to be the case in many counties [1, 2]. The widespread availability of opioids has led to an increase in opioid dependence and subsequent overdose deaths, which has continued to rise despite a decrease in opioid prescriptions in recent years [3, 4]. One hypothesis for the increase in overdose death despite a reduction in opioid prescriptions is that opioid-dependent patients are turning to illicit opioids, leading to overdose. Trends in substances found in overdose deaths support this hypothesis [3]. Federal efforts to address the opioid overdose epidemic have focused primarily on educating prescribers to reduce prescribing and increasing access to opioid addiction treatment [5]. Less attention has been paid to ensuring that evidence-based treatment for chronic pain is provided alongside opioid tapering and/or addiction treatment. Many studies have demonstrated that opioids are non-superior to several alternatives for treating chronic pain [6-8]. While opioid tapering can be a challenge for both patients and providers [9, 10], structured opioid tapering programs have demonstrated both efficacy in opioid reduction and often either unchanged or decreased pain intensity [11]. However, these results have primarily been found in specialty centers providing intensive multi-modal treatment, often treating patients 8 hours per day for 5 days a week. Given the scarcity of such programs and the high prevalence of opioid-dependent patients, alternative care-models capable of greater scaling will be necessary to address the current epidemic.

**Collaborative Care is a healthcare model capable of providing specialty care to far more patients than can be achieved through traditional one-on-one treatment models.** Collaborative Care has proven effective in delivering treatments for managing depression and pain in primary care settings [12-15]. A few recent studies have also demonstrated efficacy in treating addiction and opioid dependence using a collaborative care approach [16, 17]. Several different pain interventions have been effective in these collaborative care trials, including medication optimization, cognitive behavioral therapy, and several different structured self-management programs. Recently, pain researchers have found positive psychology-based interventions to be effective, well-received, and easy to deliver [18-20], making this intervention well-suited to pair with collaborative care. In the proposed clinical trial, we will assess the feasibility of utilizing collaborative care to facilitate opioid tapering in patients with chronic pain using a positive psychology intervention.

**Primary Aim:** Determine the potential effectiveness of delivering Collaborative Care for reducing opioids in patients with chronic pain.

**Hypothesis:** Collaborative Care will be effective (30% reduction in mean morphine equivalent dose/day [MMED]) in reducing opioids while maintaining pain control (< 1 point increase in 0 to 10 pain rating scale).

**Secondary Aim:** Assess adherence to tapering and satisfaction of patients with this Collaborative Care approach.

**Hypothesis:** Patients will be satisfied with (mean score  $\geq 3$  on 0 to 5 satisfaction scale) and adhere to ( $\geq 70\%$  retention) the 12-week opioid tapering program.

**Impact of this research.** Excessive prescribing of opioid medications for chronic pain has led to widespread opioid dependence, abuse, and rising overdose deaths. Preliminary research by others has demonstrated that multidisciplinary specialty care for patients with chronic pain on opioid therapy can produce successful opioid tapering without worsening of pain or mood symptoms. However, reducing opioid prescribing for chronic pain in the primary care setting has proven difficult given limited visit time, inadequate provider training, and constrained clinic resources for managing patients with opioid dependence [9, 10, 21]. This trial proposes a novel collaborative care approach for opioid weaning using proven, easy-to-deliver positive psychology tools for pain management that, if successful, could be implemented broadly in many clinics struggling to safely reduce opioid prescribing.

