**Table 1. Previous Work by Team Relevant to CCODAP Trial**

Trial	[name] Role	N	Mo.	Symptoms Targeted	Patient Sample	Tele-care	Intervention	Benefits
AIM[25]	Co-PI	176	9	Depression	Neurology (stroke)	Partly	Medications	Intervention > Usual care
SCAMP[26, 27]	PI	250	12	Pain Depression	Primary care	Partly	Medications & Self-management	Intervention > Usual care
INCPAD[13, 28]	PI	405	12	Pain Depression	Cancer (all types)	Fully	Medications	Intervention > Usual care
SCOPE[14, 29]	PI	250	12	Pain	Primary care	Fully	Medications	Intervention > Usual care
CAMMPS[15, 30]	PI	300	12	Pain, Anxiety, Depression	Primary care	Fully	Medications & Self-management	NCM + ASM > ASM alone†
COPE[31, 32]	Co-Invest	495	6	Function Pain	Cancer (advanced)	Partly	Physical therapy & Pain management	Intervention > Monitoring only
SPACE[8, 33]	Co-Invest	240	12	Pain	Primary care	Partly	Medications	Non-opioids = Opioids
ESCAPE[34]	Co-Invest	241	9	Pain	Primary care	Partly	Medications + CBT	Intervention > Usual care

† NCM = nurse care management, ASM = automated symptom management

**Study Design.** Forty patients with non-cancer chronic pain on long-term oral opioid therapy will be recruited into this pilot trial. Patients will be randomized to receive either the treatment intervention (n = 20) or usual care (n = 20). Assignment to treatment arm will be determined by a computer-generated randomization list in permuted blocks of 4 to maintain balanced assignment throughout the trial. Participants must: (1) be age 18 or older, (2) have an established chronic pain disorder of at least 6 months, and (3) be receiving chronic daily oral opioid treatment. Exclusion criteria are: (1) not speaking English, (2) significant cognitive impairment that would hinder participation.

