### Usual care arm:

Patients randomized to usual care will continue to receive care from their primary physician, with no active involvement by study personnel. Patients in this group will fill out the same baseline and 12 week questionnaires as patients in the intervention arm.

**Outcome measures.** In addition to demographic and clinical characteristics that will be assessed at baseline, numerous symptom measures will be assessed at baseline and at the conclusion of 3 months of treatment (Table 3). Participants will receive a \$40 gift card for each of the two outcome interviews (baseline and conclusion) that they complete. Opioid daily dose reduction is the primary outcome and will be measured in morphine-equivalent daily dose (MEDD). Secondary outcomes will include pain intensity, pain interference, positive affect, depression, anxiety, and disability. We will attempt to collect follow-up questionnaire data for up to 3 additional months after the conclusion of the trial to maximize the likelihood of data capture.

**Qualitative Interview.** At the conclusion of the study, participants will be invited to participate in semi-structured individual interviews to discuss their experience with chronic pain and the trial, what worked well, what could be improved, and potential strategies to bolster recruitment of additional patients in future studies. We will aim to conduct interviews of 10 patients in the intervention arm. Each interview will be audiotaped, transcribed, and independently analyzed by 2 reviewers to determine key themes related to barriers and facilitators using qualitative methods used in previous trials by [name] [49, 50]. Participants will receive a \$50 gift card for completion of a qualitative interview.

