**Data Analysis Plan.** Descriptive statistics (means, medians, standard deviations, inter-quartile ranges, and frequencies) will be computed to assess variables' distributional properties and to describe the sample when disseminating results. Since this is a small pilot study to test feasibility and patient acceptance, it is not formally powered to test a specific treatment effect size. Instead, whatever treatment effect is found will be useful in planning the sample size for a more definitive trial. However, a sample of 20 participants per arm has 80% power with an alpha of .05 to detect a 30 mg MEDD greater dose reduction in the intervention group (e.g., from 70 MMED to 40 MMED) assuming a SD for the MEDD of 30[8] and 20% attrition (i.e., 32 of the 40 participants completing the trial). We will also explore treatment effect moderators, including medical comorbidity (using a 9-item checklist), personality (TIPI scores), baseline pain interference, pain catastrophizing, pain self-efficacy, baseline somatic symptoms (SSS-8), mental health (PROMIS depression and anxiety), and baseline opioid difficulties (PODS).

**Feasibility.** Several factors support the feasibility of our trial. First, as noted in the Preliminary Work section (**Table 1**), our team has successfully conducted multiple telecare-centered intervention trials [8, 13, 15, 25-33, 51]. Second, several of these trials have demonstrated efficacy in managing pain [8, 13, 15, 25-33, 51]. Third, we will be utilizing a positive psychology intervention that has been shown to improve pain outcomes in patients with chronic pain [42]. Finally, others have demonstrated success in recruiting patients for and completing an opioid tapering program [17, 35]

**Potential Problems and Alternative Approaches.** As described above, should patient recruitment prove challenging, we have several recruitment strategies. Further, adding additional clinical sites for recruitment would be another potential approach. High drop-out rates are an additional concern. If this occurs, identifying factors contributing to drop-out can inform further refinement of the treatment protocol in a subsequent study.

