**Table 3. Outcome Assessment: Measures and Schedule of Administration**

Domain	Measure	# Items	Schedule (month)	
			0	3
Primary outcome				
Opioid Daily Dose	Morphine-Equivalent Daily Dose (MEDD).	1	X	X
Secondary outcomes				
Pain	PROMIS Pain	9	X	X
Pain Catastrophizing	CSQ Catastrophizing	4	X	X
Pain Efficacy	Pain Self Efficacy Questionnaire (PSEQ)	4	X	X
Depression, Suicidality	PROMIS Depression / *P4 Screener	5	X	X
	Remission Evaluation and Mood Inventory Tool (REMIT)	5	X	X
Anxiety	PROMIS Anxiety	4	X	X
Positive Affect	Positive and Negative Affect Scale – Short Form (PANAS – SF)	10	X	X
Somatic Symptoms	Somatic Symptom Scale – 8 (SSS8)	8	X	X
Disability	Sheehan Disability Scale (SDS)	3	X	X
Opioid Problems	Prescription Opioids Difficulties Scale (PODS)	16	X	X
	PROMIS Prescription Opioid	7	X	X
	Craving State, OUD Intensity/Interference Scale (ORG)	4	X	X
Substance Use	Substance Use Questionnaire	13	X	
Medical Co-Morbidity	Chronic disease checklist	9	X	
Demographics		8	X	
Personality	Ten Item Personality Inventory (TIPI)	10	X	X
Global Rating of Change		2		X
Satisfaction with treatment		2		X

Interview time in minutes (est.)			45	45
----------------------------------	--	--	----	----

\*P4 screener only used at baseline

**Benchmarks of Success.** The following will provide benchmarks to evaluate the success of the proposed study: (1) Secure IRB approval for the study; (2) Recruit and consent the first 20 participants, conduct the interventions with these participants, and collect data; (3) Repeat with the second set of 20 participants; (4) Enter and clean the data; (5) Analyze data; (6) Write manuscript(s) and submit for publication; and (7) Develop an NIH K-23 grant application based on results of this trial.

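### The 30% dose-reduction criterion names no comparator, and the plan does not name the estimator for the between-arm effect it intends to use

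*Combined protocol and SAP*

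**What the plan says.** - **Specific Aims, Primary Aim hypothesis:** "Collaborative Care will be effective (30% reduction in mean morphine equivalent dose/day [MMED]) in reducing opioids". The criterion mentions neither usual care nor a difference between arms.
- **Study Design:** "Patients will be randomized to receive either the treatment intervention (n = 20) or usual care (n = 20").
- **Outcome measures:** "Opioid daily dose reduction is the primary outcome and will be measured in morphine-equivalent daily dose (MEDD"). The word *reduction* implies change from baseline.
- **Usual care arm:** "Patients in this group will fill out the same baseline and 12 week questionnaires as patients in the intervention arm". Table 3 schedules "Morphine-Equivalent Daily Dose (MEDD") at months 0 and 3, so control data on the primary outcome will exist.
- **Data Analysis Plan:** it covers descriptive statistics, a power statement and exploratory moderators. The pilot, it says, "it is not formally powered to test a specific treatment effect size" is the right description of, yet "whatever treatment effect is found will be useful in planning the sample size for a more definitive trial". The only sentence that compares the arms on dose is the power statement, which is framed "to detect a 30 mg MEDD greater dose reduction in the intervention group". It gives no model, baseline handling or confidence interval for that comparison.

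**The concern.** There are two linked gaps.

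First, the hypothesis attaches the word *effective* to a fall in mean dose with no comparator. Read literally, a fall that also occurred under usual care would satisfy it. The documents themselves give reason to think usual-care doses may move: Specific Aims notes that opioid prescribing has fallen in recent years, and the consent-waiver argument describes prescribers under growing pressure to cut or stop opioids. Neither statement comes with a figure for this population over 12 weeks.

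Second, the plan intends to carry the treatment effect forward into the sample size of a definitive trial. That needs a between-arm estimate with its uncertainty, from an analysis fixed before the data are seen. A change-score comparison and a baseline-adjusted model both fit the phrase *dose reduction*. With about 32 completers they can give different estimates and different precision, and leaving the choice open invites selection after the fact.

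**Working it through.** **Inputs from the documents.** 20 per arm; 20% attrition, hence 32 completers (16 per arm); SD 30 mg; target difference 30 mg; alpha .05; example baseline 70 mg. Sidedness is not stated. The plan does not say whether the SD of 30 refers to dose or to change in dose; I take it as the SD of dose at both times.

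**Assumed.** Baseline-to-week-12 correlation r = .3/.5/.7, with .9 as a limit. The documents give no value.

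**1. The plan's own figure.** The standard error of a difference in means is 30 × √(2/16) = 10.61 mg, so the standardised difference is 30/10.61 = 2.83. Two-sided power is Φ(2.83 − 1.96) = .807 by the normal approximation and .781 by the noncentral t with 30 df. The stated 80% reproduces as a two-sided, two-sample comparison of 16 completers per arm. The sample size therefore already assumes a between-arm contrast.

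**2. Precision by estimator.** Half-width of the 95% CI = t(.975, df) × SD × √(2/16), where the SD is:
- unadjusted week-12 dose: 30, df 30;
- change score: 30√(2(1 − r)), df 30;
- ANCOVA: 30√(1 − r²), df 29.

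| r | Change-score SD | Half-width | ANCOVA SD | Half-width |
|---|---|---|---|---|
| .3 | 35.5 | 25.6 mg | 28.6 | 20.7 mg |
| .5 | 30.0 | 21.7 mg | 26.0 | 18.8 mg |
| .7 | 23.2 | 16.8 mg | 21.4 | 15.5 mg |
| .9 | 13.4 | 9.7 mg | 13.1 | 9.5 mg |

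The unadjusted comparison gives 2.042 × 30 × 0.3536 = 21.7 mg at any r. The ANCOVA column ignores chance baseline imbalance, whose effect is small: closed-form power for 30 mg is 82/88/97% at r = .3/.5/.7, against 80/87/96% when imbalance is simulated. Change-score power is 64/78/94%.

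**3. Cost of leaving the choice open.** In simulation with no treatment effect, the median gap between the change-score and ANCOVA estimates from the same data is 4.7/3.3/1.9 mg at r = .3/.5/.7. Reporting whichever of the two is significant raises the 5% error to 7.7/7.3/6.8%. At r = .9 these shrink to 0.6 mg and 6.0%.

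**4. The one-arm criterion with no treatment effect.** Let both arms truly fall by a fraction f from a mean of 70 mg. The intervention arm meets the criterion if its week-12 mean is at most 0.7 times its observed baseline mean. The variance of (week-12 mean − 0.7 × baseline mean) is (1 + 0.49 − 1.4r) × 900/16, so

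P = Φ((70f − 21)/√((1.49 − 1.4r) × 56.25)).

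At r = .5 the denominator is √(0.79 × 56.25) = 6.67, giving:
- f = 0: Φ(−3.15) = 0.1%
- f = 10%: Φ(−2.10) = 1.8%
- f = 20%: Φ(−1.05) = 14.7%

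For r from .7 to .3, the 10% case runs from 0.5% to 3.6% and the 20% case from 9.6% to 18.4%. Every f is an assumption.

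**The case against.** The strongest reply is that this is a pilot that disclaims formal power, and that between-arm intent is already clear. Two randomised arms, a named primary outcome, and a power sentence with a difference, an SD and an alpha together give comparator and direction, and *treatment effect* in a randomised trial means a between-arm difference. That stands. A reader might infer that the plan contains no between-arm comparison at all; the power sentence does not allow that reading. What is missing is the estimator and how it will be reported.

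The 30% also sits beside other thresholds without a comparator: a limit on pain increase, a satisfaction score and a retention rate. The last two describe patients in the tapering programme and cannot be contrasts. It is fair to read the 30% as a pilot benchmark, though the word *effective* invites more.

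A reader might also infer that a false claim of success is likely. The documents do not support that: with no or little common fall the chance is 0.1% to 1.8% at r = .5, and no passage gives a 12-week fall under usual care.

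Finally, under randomisation the change score and ANCOVA target the same mean difference, so the preference for ANCOVA concerns efficiency, not validity. Either could be computed from the data to be collected. What is lost without a stated choice is protection from post-hoc selection, not the estimate itself. These points limit the weight of the concern; they do not supply the missing analysis.

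**Conclusion.** The point holds in a limited form. The success criterion does not use the usual-care arm that the trial randomises and measures, and the plan does not name the estimator for the treatment effect it means to carry into the next trial.

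If SD 30 applies to dose at both times and r lies between .3 and .7, baseline adjustment narrows the 95% CI half-width by 4.9/2.9/1.3 mg relative to a change score (25.6 − 20.7, 21.7 − 18.8, 16.8 − 15.5). By r = .9 the gain is 0.2 mg. The false-success risk of the one-arm reading is material only at assumed common falls of about 20% or more.

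A reader might take the mismatch between 30% and 30 mg as a power error. It is not: 80% applies to 30 mg and reproduces. A 30% between-arm difference at the example baseline would be 0.30 × 70 = 21 mg, with about 48% power unadjusted, but the plan never claims power for that difference. The change is worth making before analysis, at moderate priority given the pilot status.

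**What to change.** In the Data Analysis Plan, state the primary analysis as the between-arm difference in 12-week MEDD by randomised arm, adjusted for baseline MEDD (ANCOVA, with a log or other transformation if dose is skewed), reported with a 95% CI.

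In the Primary Aim hypothesis, base any statement of effectiveness on that contrast, and label the within-arm 30% a descriptive pilot benchmark.

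The cost is two sentences and one degree of freedom. Baseline MEDD is already collected in both arms, so no new data or visits are needed. The sample size and the power statement can stay as they are.

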## Research Strategy

### SIGNIFICANCE

**Opioid Overdose Deaths are a Public Health Emergency.** In 2016, there were over 42,245 overdose deaths involving opioids in the United States, representing a 292% increase from 2001[22] [3]. These deaths have struck the 24-35 year-old range especially hard, where 20% of deaths in 2016 in this age group were attributed to opioids, leading to 1,681,359 lost years of life [22]. This spike in overdose deaths follows a sharp increase in opioid prescribing for chronic pain, which preceded a rise in non-medical opioid use [23]. In theory, decreasing opioid prescribing to patients with chronic pain may reduce the risk of overdose to patients and the general population[24]. However, the current strategy of opioid prescription reduction actually has coincided with an increase in opioid-related overdose deaths [3].

**Opioids are non-superior to other pain-management strategies.** Although opioid medications perform better than placebo for the treatment of chronic non-cancer pain, the current evidence available does not suggest that opioids are superior to other treatments for chronic pain [6-8]. In a multidisciplinary intensive outpatient setting, patients were successful in opioid tapering without worsening pain, mood, or functioning [11].

**Managing patients with opioid dependence is a challenge in primary care settings.** Primary care providers struggle to reduce opioids for chronic pain given limited resources available to help with this [9, 10]. Despite clinical guidelines being available, insufficient time and difficulty having discussions about opioid misuse have hampered their utilization [21].

### C. INNOVATION

**CCODAP is the first trial to combine collaborative care with positive psychology pain management tools to support opioid weaning in patients with chronic pain.** This dual focus on reducing opioids while simultaneously addressing the patient's pain has been absent from many regulatory and practice initiatives which have focused solely or predominantly on opioid reduction or discontinuation as the principal benchmark.

### D. APPROACH

#### Previous Work

**Symptom management trials by study team members.** As shown in **Table 1**, the study team has a strong track record in conducting symptom management RCT's. Seven of the eight trials have focused on patients with pain. All of the trials have relied on collaborative telecare-delivered interventions, either fully/mostly (n=3) or in part (n=5). The studies have ranged from 6 to 12 months in duration and have had high retention and follow-up rates. Interventions have included medications, self-management, physical therapy, and behavioral treatments. Finally, this application's trialists have complementary expertise including internal medicine/symptom management ([name]) and psychiatry/behavioral therapy ([name]).

**Table 1. Previous Work by Team Relevant to CCODAP Trial**

Trial	[name] Role	N	Mo.	Symptoms Targeted	Patient Sample	Tele-care	Intervention	Benefits
AIM[25]	Co-PI	176	9	Depression	Neurology (stroke)	Partly	Medications	Intervention > Usual care
SCAMP[26, 27]	PI	250	12	Pain Depression	Primary care	Partly	Medications & Self-management	Intervention > Usual care
INCPAD[13, 28]	PI	405	12	Pain Depression	Cancer (all types)	Fully	Medications	Intervention > Usual care
SCOPE[14, 29]	PI	250	12	Pain	Primary care	Fully	Medications	Intervention > Usual care
CAMMPS[15, 30]	PI	300	12	Pain, Anxiety, Depression	Primary care	Fully	Medications & Self-management	NCM + ASM > ASM alone†
COPE[31, 32]	Co-Invest	495	6	Function Pain	Cancer (advanced)	Partly	Physical therapy & Pain management	Intervention > Monitoring only
SPACE[8, 33]	Co-Invest	240	12	Pain	Primary care	Partly	Medications	Non-opioids = Opioids
ESCAPE[34]	Co-Invest	241	9	Pain	Primary care	Partly	Medications + CBT	Intervention > Usual care

† NCM = nurse care management, ASM = automated symptom management

**Study Design.** Forty patients with non-cancer chronic pain on long-term oral opioid therapy will be recruited into this pilot trial. Patients will be randomized to receive either the treatment intervention (n = 20) or usual care (n = 20). Assignment to treatment arm will be determined by a computer-generated randomization list in permuted blocks of 4 to maintain balanced assignment throughout the trial. Participants must: (1) be age 18 or older, (2) have an established chronic pain disorder of at least 6 months, and (3) be receiving chronic daily oral opioid treatment. Exclusion criteria are: (1) not speaking English, (2) significant cognitive impairment that would hinder participation.

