**(4) The waiver will not adversely affect the rights and welfare of subjects.** Participants will continue to receive clinical services as usual whether or not they participate in this study, and the waiver of written consent will in no way affect this.

**(5) When appropriate, subjects will be provided with additional pertinent information after participation.** All participants will continue to receive additional pertinent information whether or not they complete a written informed consent electronic document.

**Baseline Data Collection and Orientation.** Enrollment and baseline data collection will occur in 75-minute sessions over telephone or teleconferencing software. This remote approach is especially important so long as social distancing precautions are in effect to mitigate the spread of the novel coronavirus. During the first 30 minutes of the enrollment session, participants will be provided a brief overview of the study by a member of the study team, followed by distribution and explanation of the informed consent document and an opportunity for participants to ask questions. In particular, they will be given information about opioid dependence, opioid use disorder, and the potential benefit of opioid dose reduction to improve pain and reduce adverse events. They will also be informed that opioid substitution therapy is a possibility if there is concern for opioid use disorder. Once informed consent is obtained, the next 45 minutes will provide time for participants to complete baseline measures, , and receive a \$40 gift card.

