### Telecare Intervention

We will utilize an evidence-based telecare approach to facilitate symptomatic management. We have successfully utilized this technique to manage pain, depression, and anxiety in several previous trials (Table 1). The telecare intervention consists of two main parts (1) symptom monitoring and (2) peer coach-facilitated treatment support.

During the trial, a peer coach will contact patients weekly by telephone (with or without video) to discuss how they are doing. Patients will be encouraged to share their logbook information with peers to facilitate discussion. Peer coaches will provide reinforcement and accountability for patients to keep up their symptom and positive psychology intervention logging. If patients report new or worsening symptoms, peer coaches will discuss with patients whether they have been able to use the treatments suggested at the trial start and will provide reminders to use these treatments if warranted. If the patient reports elevated distress, intolerance of symptomatic treatments, opioid cravings or opioid use disorder behaviors, the peer and participant will relay this information to the physician-investigator. If an adjustment to the treatment plan is indicated, the physician-investigator will make adjustments in collaboration with the patient's primary treating physician.

The peer coach will meet with the study PI ([name]) weekly to discuss new cases and treatment plans as well as participants for whom treatment adjustments based upon symptom monitoring may be warranted.

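### A single fixed block size of 4, with unmasked arms and no concealment step described, leaves an expected one third of allocations predictable with certainty

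*Combined protocol and SAP*

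**What the plan says.** The protocol's Study Design paragraph (section D, Approach) gives the whole randomisation method: "Assignment to treatment arm will be determined by a computer-generated randomization list in permuted blocks of 4". The ratio is 1:1, 20 patients per arm. No strata are named, and balance through the trial is given as the purpose of blocking. The documents do not say who holds the list, how an assignment is released, or whether it is released before or after baseline measures. They describe no masking of patients, staff or assessors.

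The two arms look different to anyone on the team. Under Telecare Intervention, "a peer coach will contact patients weekly by telephone (with or without video) to discuss how they are doing", and the coach meets the study PI "weekly to discuss new cases and treatment plans". Under Usual care arm, controls "will continue to receive care from their primary physician, with no active involvement by study personnel". Enrolment is also done by the team: in the baseline session, "participants will be provided a brief overview of the study by a member of the study team".

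Under Opioid Reduction, patients choose whether to attempt a lower dose. The primary outcome is reduction in daily opioid dose (MEDD). Table 3 has no item on readiness or willingness to taper.

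**The concern.** In a block of 4 with two patients per arm, the last assignment is always fixed by the first three, and sometimes the last two are fixed by the first two. The block size is written in the protocol, so the team knows it. Because the arms are visible, past assignments can be known too. A hidden list does not prevent this kind of prediction, since it needs only the block size and the sequence so far.

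If the next assignment can be foreseen, the person enrolling could bring a session forward or put it off. Patients who seemed keener to reduce their dose could then be placed in the intervention arm. Tapering is voluntary, so keenness bears directly on the primary outcome. With no baseline measure of it, an imbalance would be hard to detect or adjust for. The Data Analysis Plan intends to use the observed effect to size a definitive trial, so an inflated estimate would carry forward.

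**Working it through.** **Inputs.** From Study Design: block size 4, ratio 1:1, N = 40. From the Data Analysis Plan: difference 30 mg, SD 30, 32 completers (16 per arm). Assumed, because the documents give no figure: steering changes a patient's expected dose reduction by *s* = 2, 5 or 10 mg, upward when intervention is foreseen and downward when usual care is foreseen.

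**The plan's own figures.** 40 / 4 = 10 complete blocks, which gives exactly 20 and 20. Power with 16 per arm: (30/30) × √(16/2) − 1.96 = 0.87, so power is about 81% (78% by the exact t calculation), close to the stated 80%. The plan gives no figure for predictability.

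**Certain allocations.** Write I for intervention and U for usual care. The six orderings of a block are equally likely.

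| Orderings | Forced assignments in each |
|---|---|
| IIUU, UUII | 2 |
| IUIU, IUUI, UIIU, UIUI | 1 |

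Total forced = 2 × 2 + 4 × 1 = 8 of 6 × 4 = 24, or one third. Over 10 blocks that is 10 × 4/3 = 13.3 of 40. Each block has one or two forced assignments, so the possible range is 10 to 20; the central 95% range is 11 to 16.

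**Best-guess accuracy.** By position in the block: 1/2, 2/3, 2/3, 1. Mean = 17/24 = 70.8%, against 50% with no information.

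**Randomly varying blocks.** These figures come from simulated lists of 40, with a guesser who knows the possible sizes but not their order.

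| Scheme | Certain | Best guess correct |
|---|---|---|
| Fixed 4 | 33.3% | 70.8% |
| Random 2/4/6 | 3.8% | 70% |
| Random 4/6/8 | 2.2% to 2.5% | 68% |

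**Bias if staff act only on certain allocations.** Bias = 2 × certain share × *s*.

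| *s* (mg) | Fixed 4 | Random 4/6/8 (at 2.5%) | Random 2/4/6 |
|---|---|---|---|
| 2 | 2 × 0.333 × 2 = 1.3 | 0.10 | 0.15 |
| 5 | 2 × 0.333 × 5 = 3.3 | 0.25 | 0.38 |
| 10 | 2 × 0.333 × 10 = 6.7 | 0.50 | 0.76 |

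At 2.2%, the 5 mg entry for 4/6/8 is 0.22.

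**Bias if staff act on their best guess every time.** Bias = 2 × (2 × accuracy − 1) × *s*. At *s* = 5:

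- Fixed 4: 2 × 0.417 × 5 = 4.2 mg.
- Random 2/4/6: 2 × 0.40 × 5 = 4.0 mg.
- Random 4/6/8, at 67.7% accuracy: 2 × 0.354 × 5 = 3.5 mg.

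Against the 30 mg difference, 3.3 mg is 11% and 4.2 mg is 14%.

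**The case against.** The strongest reply is that knowledge of the sequence is inferred. The coach and PI discuss new cases, but nothing says the person enrolling is present, and the documents neither call the trial open-label nor give the size of the team. Silence about the list holder is not evidence that enrolling staff tracked assignments. This stands, and it limits the point to a risk.

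Opportunity may also be small. Most eligibility criteria are factual (age, pain duration, daily oral opioid), and Recruitment and Consent expects low referral and high refusal, so there may be few patients to reorder. This stands in part: sessions are scheduled, so timing can be moved, and dose reduction is discussed in the enrolment session itself.

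Fixed blocks of 4 also serve the stated aim of balance in a 40-patient pilot that is not formally powered. That is fair, but varying blocks give up very little balance.

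A reader might infer that the block change would remove the whole 4.2 mg. It would not: that figure comes from guessing at every allocation, and varying blocks reduce it by only about 0.2 to 0.7 mg. The simulated guesser knows the possible sizes; truly undisclosed sizes might do somewhat better, but that has not been shown.

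A reader might also infer that such bias could never be repaired in analysis. That is too absolute. Baseline MEDD, opioid difficulties, pain self-efficacy and mood are collected, so partial adjustment and imbalance checks are possible. Readiness to taper is what remains unmeasured.

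**Conclusion.** The point holds as a cheap improvement. With fixed blocks of 4, an expected one third of allocations (13.3 of 40) are certain to anyone who knows the block size and the order so far, and 71% can be guessed. Randomly varying sizes cut the certain share to about 2% to 4% but lower best-guess accuracy only to 68% to 70%.

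The predictability figures for blocks of 4 are exact expectations given that knowledge. The bias figures rest on an assumed shift of 2 to 10 mg and on staff acting on every certain allocation; with no steering the bias is zero.

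The documents do not support the inference that selection occurred, or that enrolling staff saw the sequence. A reader might also set the bias against a 21 mg target, taking 30% of the 70 mg in the power example. The plan states no such target; its only between-arm difference is 30 mg. The power calculation is unaffected.

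**What to change.** In Study Design, replace the fixed block size with randomly varying sizes, for example 4, 6 and 8. Keep the sizes out of the protocol and away from enrolling staff. Hold the list in REDCap, which the protocol already names for secure records, and state that each allocation is released only after consent, eligibility and baseline measures are recorded. If enrolment has begun, apply this to the remaining allocations and document how earlier ones were concealed.

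The cost is a new list and a short edit. Final arms may no longer be exactly 20 and 20: if a block of 8 is cut after four patients in one arm, the worst case is 22 and 18. Someone who still sees the running order could make informed guesses, so enrolling staff should also be kept from that order where staffing allows.
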